8.3.2 Handling of Missing Plasma Concentration Data or below LOQ

Plasma concentrations can only be missing if the sample was not collected. These missing concentrations will be considered as non-informative missing and will not be imputed.

However, if a plasma sample was collected, but the resulting assay failed to detect a quantifiable concentration, these will be imputed in the following way:

- Concentration values below the assay's lower limit of quantification (<lower limit of quantification (LLOQ) or below the limit of quantification (BLQ)) in pre-dose samples and

in samples taken before the time of the first quantifiable concentration will be treated as zero.

- All sample collected prior to dosing will be treated as zero.
- Post-dose BLQ values after the first quantifiable time point that are flanked and followed by quantifiable concentrations will be set to LLOQ.
- Post-dose BLQ values after the first quantifiable time point that are not followed by quantifiable concentrations will be set to LLOQ.
- For PK profiles with no values reported above the LLOQ, these BLQ values will be set to LLOQ.

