3.3 BRIEF DESCRIPTION

This is a phase I, single-center, double-blind, randomized, placebo-controlled study to evaluate the safety, tolerability, and PK of single or multiple ascending dose (SAD or MAD) of RP3128 in healthy volunteers.

There were 5 cohorts in SAD and 3 cohorts in MAD. In the first part of the study (Part 1, SAD), single dose of RP3128/placebo was administered on Day 1. In the second part (Part 2, MAD), multiple doses of RP3128/placebo were administered once a day from Day 1 to Day 7. In both SAD and MAD, the cohorts were dosed sequentially so that a minimum of 8 days was allowed between dose of previous cohort and the initiation of next cohort. Progression to the next higher dose occurred only after confirming safety, tolerability and PK of existing dose. In case of safety concern, additional subjects may be added to cohort for safety assessment as per the decision of Safety Review Committee (SRC).

In addition, sentinel design was applied. Within each cohort, 2 sentinel subjects was dosed first for safety assessment. Safety and tolerability data up to 24 hours was reviewed along with any observation up to 36 hours by the investigator prior to dosing the remaining subjects at that dose level. The remainder of the cohort was dosed sequentially at least 48 hours after confirming safety and tolerability of sentinel cohort.

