8.2 COLLECTION SCHEDULE

For SAD part, blood samples will be collected for plasma levels of RP3128 on Day 1 (Pre-dose, 0.25, 0.5, 1.0, 2.0, 4.0, 6.0, 8.0, 12.0, 24.0 and 48 hr), Day 5, Day 8 and Day 15. For MAD part, blood samples will be collected for plasma levels of RP3128 on Day 1 (Pre-dose, 0.25, 0.5, 1.0, 2.0, 4.0, 6.0, 8.0, 12.0 and 24.0 hr), Day 3, Day 5, Day 7 (Pre-dose, 0.25, 0.5, 1.0, 2.0, 4.0, 6.0, 8.0, 12.0 and 24.0 hr), Day 9 (48 hr), Day 10 (72 hr), Day 11 (96 hr), Day 12 (120 hr), Day 13 (144 hr) and Day 15 (192 hr).

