8.3 DERIVED DATA AND HANDLING OF MISSING OR BELOW LLOQ DATA

8.3.1 Derivation of PK Parameters

PK parameters for RP3128 will be derived with validated SAS programs for all RP3128 dose levels by non-compartmental analysis of the plasma concentration data using actual sampling times.

The following pharmacokinetic variables will be derived:

SAD:

- Maximum observed plasma concentration (C_{max})
- Time to maximum plasma concentration (T_{max})
- Terminal half-life ($t_{1/2}$)
- Area under the plasma concentration-time curve from time zero until the last measurable time point (AUC_{0-t})
- Area under the plasma concentration-time curve from time zero to infinity time (AUC_{0-inf})
- Elimination rate constant (K_{el})

MAD:

- Maximum observed plasma concentration in the dosing interval (C_{max}) (Day 1, Day 7)

- Lowest observed plasma concentration in the dosing interval (C_{\min}) (Day 7)
- Plasma concentration at the end of the dosing interval (C_{trough}) (Day 3, Day 5, Day 7)
- Average concentration during the dosing interval (C_{av}) (Day 7)
- Time to maximum plasma concentration (T_{max}) (Day 1, Day 7)
- Area under the plasma concentration-time curve from time zero until the last time point with measurable concentration (AUC_{0-24}) (Day 1, Day 7)
- Degree of fluctuation $[(C_{\text{max}}-C_{\min})/C_{\text{av}}]$ (Day 7)
- Swing $[(C_{\text{max}}-C_{\min})/C_{\min}]$ (Day 7)

The PK parameters will be estimated as follows:

- The C_{max} and the corresponding T_{max} , C_{\min} and C_{trough} will be read directly from the concentration-time plot (observed data, not predicted data by the program).
- AUCs will be calculated using the linear trapezoidal rule.
- The terminal elimination rate constant (K_{el}) will be determined by log linear regression obtained on at least the 3 last quantifiable concentrations and will not include C_{max} . The adjusted square of the correlation coefficient (R-square adjusted) for the goodness of fit of the regression line through the data points must be at least 0.80 for the K_{el} value to be considered reliable. If fewer than 3 quantifiable concentrations are available after C_{max} or if R-square is less than 0.80, the K_{el} will be left uncalculated.
- $t_{1/2}$ is calculated by the program as $\ln 2 / K_{\text{el}}$. If K_{el} is not calculable, then $t_{1/2}$ will also remain missing.
- The AUC from 0 to infinity is calculated by the program as:

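### SAP 8.3.2 sets BLQ pre-dose samples to zero without limiting this to the first dose, so a BLQ trough in the MAD part has no single value

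*SAP*

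**What the plan says.** Section 8.3.2 opens by restricting its list to collected samples in which "the resulting assay failed to detect a quantifiable concentration, these will be imputed in the following way". Five rules follow:

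1. Zero for values "or below the limit of quantification (BLQ)) in pre-dose samples and" for samples before the first quantifiable concentration.
2. "All sample collected prior to dosing will be treated as zero".
3. "Post-dose BLQ values after the first quantifiable time point that are flanked and followed by quantifiable concentrations will be set to LLOQ".
4. The same LLOQ value for post-dose BLQ results after the first quantifiable time point with no quantifiable result after them.
5. "For PK profiles with no values reported above the LLOQ, these BLQ values will be set to LLOQ".

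Section 3.3 describes the MAD part: "multiple doses of RP3128/placebo were administered once a day from Day 1 to Day 7". Section 8.2 lists the later MAD samples as "Day 3, Day 5, Day 7 (Pre-dose, 0.25, 0.5, 1.0, 2.0, 4.0, 6.0, 8.0, 12.0 and 24.0 hr"; Day 7 has a labelled pre-dose sample, while Days 3 and 5 have no clock time.

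Section 8.3.1 defines Cmin as "Lowest observed plasma concentration in the dosing interval" and takes Cmin and Ctrough from observed data. Table 2 in section 8.4 asks for a geometric mean and geometric CV% of both.

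**The concern.** In a single-dose study, a sample taken before dosing can only precede all drug, and zero is a natural value. In the MAD part the Day 7 pre-dose sample follows six earlier doses. It is a trough, and the zero rule still catches it when it is BLQ, because neither rule 1 nor rule 2 mentions the first dose. Section 6.2 does name the first dose when it defines baseline.

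Characterising multiple-dose PK at steady state is a MAD secondary objective. Of the nine MAD PK endpoints in section 4.2, four (Cmin, Ctrough, degree of fluctuation, swing) can depend on the value given to such a sample. Two programmers could follow the SAP and report different results.

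Two smaller points lie in the same list. Rule 2 leaves out the BLQ limit that the lead-in supplies, so coding it word for word would overwrite a measured Day 7 trough with zero. For the pre-dose sample of a profile with no quantifiable value, rules 1 and 5 give different answers.

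**Working it through.** **Inputs.** Daily dosing on Days 1 to 7 (3.3); sampling times (8.2); parameter definitions (8.3.1); summary statistics (8.4, Table 2, and the footnote to Table 14.2.1.2.2.X.M, which bases geometric means on ln-transformed values); six RP3128 subjects per MAD cohort (3.6). The SAP gives no LLOQ and no expected concentrations, so the trough values below are assumptions.

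**Step 1: apply each rule to each kind of sample.**

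| Sample | Rules 1 and 2 | Other rule | Settled? |
|---|---|---|---|
| Day 1 pre-dose, BLQ, quantifiable values later | 0 | none | yes |
| Day 7 pre-dose, BLQ, after an earlier quantifiable value | 0 | LLOQ (3, 4), if post-dose counts from the first dose | no |
| Day 3 or 5, BLQ, if drawn pre-dose, after an earlier quantifiable value | 0 | LLOQ (3, 4), same condition | no |
| Day 7 at 24 h, BLQ, after a quantifiable value | not applicable | LLOQ (4) | yes |
| Pre-dose sample of an all-BLQ profile | 0 | LLOQ (5) | no |
| Later MAD pre-dose sample, quantifiable | outside the list, by the lead-in | observed value (8.3.1) | yes, though rule 2's own words omit the limit |

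**Step 2: Day 7 parameters, if the pre-dose sample counts towards Cmin.**

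- Swing = (Cmax − Cmin)/Cmin. With Cmin = 0 it is undefined; with Cmin = LLOQ it is (Cmax − LLOQ)/LLOQ.
- Fluctuation = (Cmax − Cmin)/Cav. Zero instead of LLOQ raises it by about LLOQ/Cav.
- AUC0-24 by the linear trapezoidal rule: the 0 h value carries weight 0.25/2 = 0.125 h, so zero instead of LLOQ lowers AUC by 0.125 h × LLOQ. Cav = AUC0-24/24 is hardly affected.

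**Step 3: summary statistics, one BLQ trough among six.** The geometric mean is exp(mean of ln values), and ln(0) does not exist. Take LLOQ = 1 unit and the other troughs as 2, 3, 4, 5 and 6.

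- Zero: mean = 20/6 = 3.33, SD 2.16; geometric mean undefined, or 720^(1/5) = 3.73 on n = 5 if the zero is dropped.
- LLOQ: mean = 21/6 = 3.50, SD 1.87; geometric mean 720^(1/6) = 2.99 on n = 6.
- Shift in the arithmetic mean: 3.50 − 3.33 = 0.17 = LLOQ/6.

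**Step 4: vary the assumption.** If the other five troughs all equal T × LLOQ, the n = 6 geometric mean divided by the n = 5 one is T^(5/6)/T = T^(−1/6).

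- T = 2: 0.891, or 11% lower.
- T = 5: 0.765, or 24% lower.

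**Step 5: what stays out of reach.** Ctrough is the concentration at the end of the dosing interval. If Day 7 Ctrough is the 24 h sample, the zero rule does not touch it. An all-BLQ profile yields no PK parameters, so the clash of rules 1 and 5 reaches only the concentration tables.

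**The case against.** The best reply is that the schedule's labels resolve the conflict. Rules 3 and 4 speak of post-dose values, and section 8.2 labels the Day 7 sample pre-dose. By label the rules do not overlap, rule 1 governs, and only the unlabelled Day 3 and Day 5 samples stay open. This is a fair reading, and it weakens the claim of a contradiction. It does not rescue the rule. On that reading a BLQ trough at the start of the Day 7 interval is zero, while a BLQ value at the end of the same interval is LLOQ, although both are 24 h after a dose. The zero still breaks swing and the geometric statistics if it enters Cmin or Ctrough.

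A reader might infer something stronger: that rule 2 orders measured troughs to be replaced by zero, which would greatly inflate fluctuation. The document does not support this. The lead-in and the section title confine the whole list to samples without a quantifiable result, and section 8.3.1 takes Cmin and Ctrough from observed data. Applied to measured troughs, the rule would also empty endpoints that the SAP itself sets up. That rule 2 adds nothing to rule 1 once it is read as BLQ-only is weak evidence of a wider meaning, since rules 3 and 4 also reach one result by two routes. What remains is that rule 2's words invite the mistake.

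It is also fair to say that nothing in the SAP shows that a 24 h trough will be BLQ. The practical effect may be nil.

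**Conclusion.** The point holds as a minor one. Section 8.3.2 does not limit its zero rule to the first dose and gives no precedence, so a BLQ pre-dose sample after Day 1 of the MAD part can be zero or LLOQ. For one such trough in six, the arithmetic mean moves by LLOQ/6. Under zero the geometric mean is undefined or drops to n = 5; in the illustrations with T = 2 and T = 5, the n = 6 value under LLOQ is 11% or 24% below that n = 5 value.

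This depends on three conditions: a trough is BLQ; Days 3 and 5 are drawn pre-dose, for their Ctrough to be affected; and the Day 7 pre-dose sample counts towards Cmin, for swing and fluctuation to be affected. Only descriptive secondary PK is involved. The loose wording of rule 2 is a secondary drafting risk, and the all-BLQ conflict a smaller one still.

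**What to change.** Amend section 8.3.2 as follows:

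- Limit the zero rule to samples taken before the first dose on Day 1, by rewording or deleting rule 2 and adding the same limit to rule 1.
- State that quantifiable pre-dose samples on later MAD days keep their measured value.
- Give one rule for BLQ troughs after the first dose, for example LLOQ as in rules 3 and 4. Cmin and Ctrough would then be above zero in any subject with a quantifiable Day 7 profile, and swing and the geometric statistics would be defined.
- State which rule governs the pre-dose sample of an all-BLQ profile.

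The cost is a few lines of SAP text and of the PK program. No new data are needed.

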 $AUC_{0-\text{inf}} = AUC_{0-t} + AUC_{t-\text{inf}}$ where t is the sampling time point of the last measurable concentration. $AUC_{t-\text{inf}}$ is calculated by the program as: C_t / K_{el} , where C_t is the observed concentration at time t and K_{el} is the elimination rate constant during the apparent terminal elimination phase. If K_{el} is not calculable, $AUC_{0-\text{inf}}$ will be set to missing.
- The AUC extrapolation to infinity ($AUC_{t-\text{inf}}$) must be $\leq 20\%$ of the total area for $AUC_{0-\text{inf}}$ to be considered reliable.

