8.5 DATA PRESENTATION

The actual sampling time of PK blood sample collection will be listed for each cohort and will include the deviation in time from the protocol scheduled time, if applicable.

Individual subject plasma concentration data will be listed by subject, time point and treatment and will be summarized at each time point by treatment group for the Safety population. Individual subject PK parameters will be listed in a table by subject and will be summarized by treatment group for the PK population.

PK parameters of secondary interest, namely R-square adjusted, the number of data points used for estimating K_{el} , the upper and lower time point used for estimation of K_{el} , and the % AUC extrapolation from t_{last} (last time point of blood draw) to infinity will be listed by subject and dose level/cohort to enable verification of the exclusions, if any, of data from the summary statistics of the PK parameters of primary interest.

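### Section 8.3.2 sets trailing BLQ concentrations to LLOQ without saying where the imputed values are used, which conflicts with the AUC definitions and puts an LLOQ floor under late mean concentrations

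*SAP*

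**What the plan says.** **BLQ handling (SAP 8.3.2).** After the last quantifiable sample: "Post-dose BLQ values after the first quantifiable time point that are not followed by quantifiable concentrations will be set to LLOQ". For a profile with nothing quantifiable: "For PK profiles with no values reported above the LLOQ, these BLQ values will be set to LLOQ". Neither rule is restricted to summaries, and neither excludes AUC. The section sits under heading 8.3, which covers both derived data and BLQ handling.

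**Parameter derivation (SAP 8.3.1).** AUC0-t is defined as "Area under the plasma concentration-time curve from time zero until the last measurable time point", and "AUCs will be calculated using the linear trapezoidal rule". For AUC0-inf the break point is given by "where t is the sampling time point of the last measurable concentration", and C_t "is the observed concentration at time t". Kel comes from "log linear regression obtained on at least the 3 last quantifiable concentrations".

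**Presentation (SAP 8.5).** The percentage of AUC extrapolated starts from t_last, which is glossed as the "last time point of blood draw) to infinity will be listed by subject".

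**Sampling (SAP 8.2 and shell of Table 14.2.1.1.X.S).** SAD samples run from pre-dose to 48 h, then Days 5, 8 and 15. The shell labels these last three as 96, 168 and 336 h.

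**The concern.** The sections give two end points for the same area. Section 8.3.1 points to the last measurable concentration. Section 8.5 points to the last draw, whether or not that sample was quantifiable. Section 8.3.2 gives every late BLQ sample a positive number, and the SAP never says whether that number counts as measurable. It uses measurable for AUC and quantifiable for Kel and BLQ handling, and defines neither. Two programmers could derive different AUCs from the same samples.

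If the imputed values enter the SAD derivation, AUC0-t runs flat at LLOQ to Day 15. The tail is roughly a fixed number of LLOQ-hours, so it weighs most, relative to AUC, where concentrations are lowest. That would distort the exposure pattern across 25-400 mg. AUC0-t and AUC0-inf are SAD secondary endpoints.

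The by-time concentration summaries have a separate problem that does not depend on where AUC stops.

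**Working it through.** **Sampling times.** Nominal time = (Day - 1) x 24, so Day 5 = 96 h, Day 8 = 168 h and Day 15 = 4 x 84 = 336 h. This matches the table shell.

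**Assumptions, because the SAP gives neither LLOQ nor half-life.** One-compartment oral model, ka = 1/h, dose-proportional; Cmax is the highest scheduled sample. Concentration is proportional to exp(-kt) - exp(-t), with k = ln 2 / half-life. All areas use the linear trapezoid on the SAD times.
- Reading A: stop at the last quantifiable sample.
- Reading B: set later BLQ samples to LLOQ and integrate to 336 h.

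**Ratio B/A for AUC0-t**

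| Half-life | LLOQ 1% of Cmax | LLOQ 5% of Cmax |
|---|---|---|
| 6 h | 1.37 | 2.45 |
| 12 h | 1.22 | 1.74 |
| 24 h | 1.12 | 1.34 |
| 48 h | 1.13 | 1.18 |
| 72 h | 1.00 | 1.25 |

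At 72 h the ratio stays at 1.00 up to LLOQ at 4% of Cmax, because the 336 h sample is still quantifiable. At LLOQ 0.25-0.5% of Cmax, as at a higher dose, the ratio is 1.00-1.12 for half-lives of 6-48 h.

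**One case by hand (harsher than the table).** Half-life 12 h, Cmax at 25 mg = 10 x LLOQ, so LLOQ is 10% of Cmax at that dose. Here k = 0.0578/h, and concentrations are in LLOQ units.
- 25 mg: the peak sample is at 4 h. C(24) = 10 x 0.2500/0.7754 = 3.22, which is the last quantifiable value. Reading A gives 156.1. The tail is 24 x (3.22 + 1)/2 + 288 x 1 = 50.7 + 288 = 338.7. Reading B gives 494.8, or +217%.
- 400 mg: C(48) = 16 x 3.22/4 = 12.9 is the last quantifiable value. Reading A gives 3271.2. The tail is 48 x (12.9 + 1)/2 + 240 x 1 = 573.6. Reading B gives 3844.7, or +18%.
- 400/25 mg ratio of AUC0-t: 3271.2/156.1 = 21 under A and 3844.7/494.8 = 7.8 under B, for a 16-fold dose ratio. Reading A is not exactly 16 because the two doses stop at different samples.
- Across 25, 50, 100, 200 and 400 mg the relative excess is 217, 74, 42, 26 and 18%. The absolute excess is 339, 303, 341, 419 and 574 LLOQ-hours.

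**By-time means.** In the same 25 mg case the model concentration is 3.22/4 = 0.81 at 48 h and 0.81/16 = 0.05 at 96 h. Both are entered as 1.0, as are 168 h and 336 h. A declining curve is reported as a plateau at LLOQ.

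**All-BLQ profile.** With pre-dose at zero and LLOQ from 0.25 h, integrating to 336 h gives 0.25/2 + 335.75 = 335.9 LLOQ-hours for a subject with no quantifiable drug.

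**The case against.** The strongest reply is that section 8.3.1, read literally, already prevents the tail. A sample in which the assay found nothing quantifiable is not measurable in ordinary language, C_t is observed, and Kel uses quantifiable values. On that reading the AUC tail is zero at every dose. Much of this stands, and it rules out several stronger inferences.

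- *Imputation comes before derivation.* A reader might infer this from the shared heading 8.3, but the SAP states no order of steps.
- *C_t becomes LLOQ at 336 h.* The word observed in 8.3.1 contradicts this.
- *Kel is contaminated.* Its wording already protects it.
- *MAD AUC0-24 has the same problem.* The interval ends at 24 h. Under the same model, single dose, half-life 6-48 h and LLOQ 0.25-5% of Cmax, the 24 h sample is always quantifiable and the ratio is 1.00.
- *The tail is largest at low doses in every sense.* This holds only relative to AUC. In the worked case the absolute excess is largest at 400 mg.

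Nor is all the excess false. With a long half-life, reading A itself misses real exposure: at 48 h the imputed AUC is only 6-10% above the model's true AUC0-inf.

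The literal reading still does not close the matter. Section 8.5 contradicts it on t_last, and 8.3.2 carries no exclusion. The LLOQ rule must also apply somewhere. If it does not apply to AUC, it applies to the by-time summaries, where the upward bias remains.

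**Conclusion.** The point holds as an unresolved conflict between 8.3.2 and 8.5 on one side and 8.3.1 on the other, together with an LLOQ floor under late by-time concentrations. It is not shown that the planned AUC will be inflated.

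If imputed values enter the SAD derivation, AUC0-t rises about 1.1- to 2.5-fold for half-lives of 6-48 h with LLOQ at 1-5% of Cmax, and by nothing if drug is still quantifiable at 336 h. More extreme figures, such as +217% at 25 mg, need LLOQ at 10% of Cmax. All sizes rest on an assumed LLOQ, half-life, ka and dose proportionality.

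PK is secondary and descriptive, so the primary safety analyses are untouched. The all-BLQ rule matters mainly for the concentration summaries, which use the Safety population; the PK population already requires enough data to determine parameters.

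**What to change.** 1. In 8.3.2, replace substitution by LLOQ for trailing BLQ values and all-BLQ profiles with exclusion from AUC0-t, AUC0-inf and Kel. For Kel this only confirms what 8.3.1 implies.
2. In 8.3.1, state that AUC0-t ends, and C_t is taken, at the last observed concentration at or above LLOQ.
3. In 8.5, redefine t_last as the time of that concentration.
4. For by-time summaries only, name a substitution other than LLOQ, for example zero.

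The cost is a few sentences and one programming rule. Late mean concentrations become slightly lower, and zero errs downward where true values lie just under LLOQ, so the convention should be stated with the tables.

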8.4 DATA SUMMARIZATION

PK parameters and plasma concentration data will be summarized by treatment using the following descriptive statistics (Table 2):

Table 2. PK Summary Statistics

Variable	Summarized with:
Plasma concentration at each time point	n, arithmetic mean, SD, CV%, minimum, median and maximum
AUCs, C _{max} , C _{min} , C _{trough} , C _{av}	n, arithmetic mean, SD, CV% (calculated as 100%*SD/mean), minimum, median, maximum, geometric mean and geometric CV% (calculated as $CV = 100\% \times \sqrt{e^{z^2} - 1}$, where z^2 is the variance of ln(PK parameter))
t _{1/2} , K _{el} , T _{max} , degree of fluctuation, swing	n, arithmetic mean, SD, CV%, minimum, median, maximum

Samples taken outside the sampling windows may be excluded from by-time point summary statistics; this will be determined prior to unblinding.

8.5 DATA PRESENTATION

The actual sampling time of PK blood sample collection will be listed for each cohort and will include the deviation in time from the protocol scheduled time, if applicable.

Individual subject plasma concentration data will be listed by subject, time point and treatment and will be summarized at each time point by treatment group for the Safety population. Individual subject PK parameters will be listed in a table by subject and will be summarized by treatment group for the PK population.

PK parameters of secondary interest, namely R-square adjusted, the number of data points used for estimating K_{el} , the upper and lower time point used for estimation of K_{el} , and the % AUC extrapolation from t_{last} (last time point of blood draw) to infinity will be listed by subject and dose level/cohort to enable verification of the exclusions, if any, of data from the summary statistics of the PK parameters of primary interest.

